7.1 Efficacy Endpoints

The changes from baseline (see sec. 8.7) and from week 8 in total maximal chorea score and total motor score from the UHDRS motor assessment are the efficacy endpoints for this study.

7.2 Safety Endpoints

Safety and tolerability will be assessed throughout the study by monitoring the following:

- Incidence of adverse events (AEs), serious AEs (SAEs), severe AEs, drug-related AEs, and AEs leading to withdrawal during the following periods:
 - The entire post-baseline period
 - During the Titration Period (from Day 1 to the end of Week 8) in Rollover subjects
 - During the Dose-Adjustment Period (from Day 1 to the end of Week 4) in Switch subjects
 - During the Extended Dose-Adjustment Period (from Day 1 to the end of Week 8) in Switch subjects who undergo dose adjustment between Weeks 4 and 8 (if at least 10% of Switch subjects have had a dose adjustment between Week 4 and Week 8)
 - During the Stable-Dose Period (Week 8 to end of study)
- Observed values and changes from baseline in clinical laboratory parameters (hematology, chemistry, and urinalysis)
- Observed values and changes from baseline in vital signs
- Observed values in ECG parameters and abnormal findings

- Numbers of subjects with QTcF values > 450 msec, > 480 msec, > 500 msec
- Counts and percentages for Columbia Suicide Severity Rating Scale (C-SSRS)
- Observed values and changes from baseline in the following:
 - Unified Huntington Disease Rating Scale (UHDRS)
 - Unified Parkinson's Disease Rating Scale (UPDRS) (dysarthria)
 - Barnes Akathisia Rating Scale (BARS)
 - Hospital Anxiety and Depression Scale (HADS)
 - Epworth Sleepiness Scale (ESS)
 - Montreal Cognitive Assessment (MoCA[®])
 - Swallowing Disturbance Questionnaire (SDQ)
- Duration of time to achieve a stable dose of SD-809, defined as the number of days from Day 1 until the first day at which the subject was taking the dose level they were receiving at Week 8.

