8.8 Time Periods for Analyses

Some analyses will be performed by time period. For these analyses, the following definitions will be used:

- Screening Period (Switch subjects only) - from informed consent until the first dose of study drug
- Dose-Adjustment Period (Switch subjects only) – Baseline through Week 4
- Extended Dose-Adjustment Period (Switch subjects only) – Baseline through Week 8
- Titration Period (Rollover subjects only) – Baseline through Week 8
- Stable-Dose Period - from Week 8 through the last dose of study drug
- Entire Treatment Period - Baseline through last dose of study drug
- Follow-up Period - from the last dose of study drug through the end of the study

Subjects who withdraw from the study during the Titration Period or the Extended Dose-Adjustment Period will not have a Stable-Dose Period. For the analyses of adverse events, to be conservative, all follow-up adverse events will be counted as events that occurred during the last available treatment period prior to the Follow-up period.

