9.9.1 Adverse Events

Adverse events will be coded using version 16.1 of the Medical Dictionary for Regulatory Activities (MedDRA); the MedDRA version will be noted in the CSR. Treatment-emergent AEs (TEAEs) are events that 1) begin after treatment with study drug in the current study and that are not present at baseline or 2) if present at baseline, have worsened in severity. For AEs with missing start dates, the AE will be considered treatment-emergent unless there is additional information indicating that the AE started prior to the first treatment. All analyses of TEAEs will be performed separately for TEAEs that occurred during the titration period (for Rollover subjects only), during the dose-adjustment period (for Switch subjects only), during the extended dose-adjustment period (for Switch subjects only), during the stable dose period, and during the entire treatment period. To be conservative, all adverse events that occurred during the follow-up period will be counted as events that occurred during the last available treatment period. In order to be included in the analysis for a given time period, a subjects must have at least one visit during the time period.

For the Switch cohort, an overview of AEs occurring during the Screening period will present the number and percentage of subjects in the following categories:

- Any AEs
- Any serious AEs (SAEs)
- Any severe AEs
- Any AE(s) leading to death

An overview of TEAEs will present the number and percentage of subjects in the following categories:

- Any TEAEs
- Any serious TEAEs

-
- Any severe TEAEs
 - Any treatment-related TEAEs
 - Any TEAEs resulting in dose reduction
 - Any TEAEs resulting in dose suspension
 - Any TEAEs resulting in withdrawal from the study
 - Any treatment-related TEAEs resulting in withdrawal from the study
 - Any TEAEs resulting in dose reduction, dose suspension, or withdrawal from the study
 - Any TEAE(s) leading to death

TEAEs, serious TEAEs, TEAEs that led to dose reduction, TEAEs that led to dose suspension, TEAEs that led to withdrawal from the study, TEAEs that occurred in at least 4% of Rollover or Switch cohort subjects in the Safety Population across all time periods, will be summarized at the subject level by MedDRA system organ class (SOC) and preferred term using frequencies and percentages.

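### SAP 7.2 limits the Switch Extended Dose-Adjustment Period to dose-adjusted subjects and a 10% trigger, conditions absent from 8.8 and 9.9.1; if 7.2 governs, Week 4–8 adverse events of non-adjusted Switch subjects fall in no sub-period table

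*SAP*

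**What the plan says.** SAP 7.2 lists the periods over which adverse-event incidence is reported. For Switch subjects there are four:

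- the whole follow-up: "The entire post-baseline period";
- the first four weeks: "During the Dose-Adjustment Period (from Day 1 to the end of Week 4) in Switch subjects";
- the Extended Dose-Adjustment Period, Day 1 to the end of Week 8, reported "in Switch subjects who undergo dose adjustment between Weeks 4 and 8" and subject to a further condition: "if at least 10% of Switch subjects have had a dose adjustment between Week 4 and Week 8";
- the later phase: "During the Stable-Dose Period (Week 8 to end of study").

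SAP 8.8 defines the time periods for analysis. Its entry reads "Extended Dose-Adjustment Period (Switch subjects only) – Baseline through Week 8", with no restriction to adjusted subjects and no trigger. The same section states that a subject who withdraws during this period has no Stable-Dose Period, and that follow-up events are counted in the last available treatment period.

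SAP 9.9.1 requires all analyses of treatment-emergent adverse events to be done separately by period, including "during the extended dose-adjustment period (for Switch subjects only), during the stable dose period". It also carries neither condition. Its only entry rule is at least one visit in the period. Neither 8.8 nor 9.9.1 refers back to 7.2.

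**The concern.** The same named period has a conditional, restricted population in one section and an unconditional one in two others. Two programmers working from this SAP could produce tables with different denominators, or one of them could produce no table.

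The choice matters because the other two Switch sub-periods leave a hole: one ends at Week 4 and the next starts at Week 8. Only the extended period fills it. The Rollover cohort has no such hole, because its Titration Period runs to Week 8 without a condition.

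Under 7.2 the denominator also depends on something that happens after baseline. SAP section 4 allows adjustment after Week 4 when clinically indicated, and bases adjustments during long-term treatment on adverse-event reports, chorea control, rating scales and safety evaluations. A group picked because its dose changed is therefore picked partly on the outcome being tabulated. Safety of switching from tetrabenazine is a stated study objective, so this cohort's early adverse-event tables deserve a single, fixed definition.

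**Working it through.** The plan states no figure that can be reproduced here. The 10% is a rule, and SAP 8.2 says that the sample size has no statistical basis. The check is a comparison of text followed by counting.

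**Coverage of Weeks 4–8 for a Switch subject whose dose was not adjusted in those weeks**

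| Period | If 7.2 governs | If 8.8 and 9.9.1 govern |
|---|---|---|
| Dose-Adjustment | ends Week 4 | ends Week 4 |
| Extended Dose-Adjustment | does not apply | covers Weeks 4–8 |
| Stable-Dose | starts Week 8 | starts Week 8 |
| Entire period | covers Weeks 4–8 | covers Weeks 4–8 |

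**Trigger.** Input: about 36 Switch subjects (protocol synopsis and section 3). 0.10 × 36 = 3.6, so 4 adjusted subjects are needed: 4/36 = 11.1% passes and 3/36 = 8.3% fails.

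**Subjects with no Week 4–8 sub-period if 7.2 governs.** This is 36 when the trigger is not met, and 36 minus the number adjusted when it is. Person-weeks are subjects × 4, out of 36 × 4 = 144, assuming no withdrawals.

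| Adjusted in Weeks 4–8 | Table produced? | Subjects not covered | Person-weeks not covered |
|---|---|---|---|
| 0 to 3 | no | 36 (100%) | 144 |
| 4 | yes | 32 (89%) | 128 |
| 9 | yes | 27 (75%) | 108 |
| 18 | yes | 18 (50%) | 72 |

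Under 8.8 and 9.9.1 the number not covered is 0 in every row.

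**Chance that the table appears.** The documents give no adjustment rate, so a range is assumed. With N = 36, the binomial probability of at least 4 adjusted subjects is 0.10 at a true rate of 5%, 0.49 at 10%, 0.81 at 15%, 0.95 at 20% and 0.998 at 30%.

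**Effect of selection.** Let q be the adverse-event risk among all Switch subjects, a the probability of adjustment given an event, and b the probability given no event. Incidence in the 7.2 group is q·a / [q·a + (1 − q)·b]. With q = 0.25 (assumed, as are all values of a and b):

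- a = 0.50, b = 0.15: 0.125 / (0.125 + 0.1125) = 53%
- a = 0.60, b = 0.10: 0.150 / (0.150 + 0.075) = 67%
- a = 0.15, b = 0.50, where doses change mainly for chorea control: 0.0375 / (0.0375 + 0.375) = 9%
- a = b: 25%

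The 8.8 definition returns 25% in all four cases.

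**Knock-on in 8.8.** Take a non-adjusted Switch subject who withdraws at Week 6. Under 7.2 that subject has no extended period, so among the sub-periods the follow-up events go back to the one that closed at Week 4. Under 8.8 they go to the extended period.

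**The case against.** The strongest reply is that the sections directing the analysis are 8.8 and 9.9.1, and both are unconditional. The withdrawal rule in 8.8 also works naturally only if every Switch subject has an extended period. A programmer who follows sections 8 and 9 produces tables with no gap and no selected denominator, and 7.2 is then leftover wording in an endpoint list. This stands to the extent that the harm depends on 7.2 governing. It does not settle the matter: 7.2 can equally be read as the specific rule that narrows the general one, and the SAP gives no order of precedence.

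A reader might also infer that four weeks of switch safety could go unreported. The documents do not support that. The entire period is always analysed, with the Switch Cohort summarised separately (SAP 8.7). Section 9.9.1 gives exposure-adjusted rates for Switch subjects, and complete adverse-event listings are provided. Only the sub-period tables are affected.

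A reader might further infer that selection under 7.2 inflates adverse-event incidence. That is not established either. Doses may move up or down, and chorea control counts as well as adverse events, so the bias could run in either direction or be absent. Describing events among subjects who had prolonged adjustment is legitimate in a single-arm, descriptive study. It is simply not an incidence for the Switch cohort.

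**Conclusion.** The inconsistency is real and explicit in the text. Its consequence is conditional. If 7.2 governs, Week 4–8 adverse events of non-adjusted Switch subjects (of all Switch subjects when fewer than 4 of about 36 are adjusted) fall in no sub-period table. Any table produced then describes a subgroup selected after baseline, which does not estimate cohort incidence, and the direction of bias cannot be determined from the documents. If 8.8 and 9.9.1 govern, neither problem arises.

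The 89% should not be read as an expected loss. It is the case exactly at the trigger, and the share falls to 50% if 18 are adjusted. The counts rest on the planned, approximate cohort size. The trigger probabilities and the selection figures rest on assumed rates and only illustrate the range. The point deserves correction because the conflict is specific and easily removed, although no adverse event is lost under either reading.

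**What to change.** In SAP 7.2, change the population of the Extended Dose-Adjustment Period from "in Switch subjects who undergo dose adjustment between Weeks 4 and 8" to all Switch subjects, and delete the bracketed 10% condition. The entry then covers Day 1 to the end of Week 8 for the whole Switch cohort, in line with 8.8 and 9.9.1, and the withdrawal and follow-up rules in 8.8 apply to every Switch subject in the same way. If a summary of subjects adjusted between Weeks 4 and 8 is still wanted, keep it as a supplement labelled as a post-baseline subgroup.

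The text change is confined to one entry in 7.2. In output, the cost is more than a single table: it is the set of treatment-emergent adverse-event tables that 9.9.1 already requires by period, now always produced for this one. No new data are needed.

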Research Advance Directive (if applicable), some data collected in the SD-809-C-15 study will be utilized in the SD-809-C-16 study and will provide some of the baseline data for SD-809-C-16 (See Schedule of Events B). In addition to assessments completed for the SD-809-C-15 Week 13 visit, evaluations required as part of the SD-809-C-16 study will be completed on the same day as the Week 13 visit. All subjects are expected to rollover to SD-809-C-16 at the Week 13 visit of SD-809-C-15.

As Rollover subjects will have discontinued study drug (SD-809 ER or placebo) for 1 week at completion of the SD-809-C-15 study, they will undergo titration on SD-809 ER. During titration, the investigator, in consultation with the subject and caregiver, will determine when an adequate level of chorea control has been achieved. The dose of SD-809 ER may be adjusted (upward or downward), in increments of 6 mg per day (each week) (6 mg/day or 12 mg/day after a total daily dose of 48 mg is reached), until there is adequate control of chorea; the subject experiences a protocol defined “clinically significant” adverse event (defined as related to study medication and either a) moderate or severe in intensity or b) meets the criteria for a Serious Adverse Event [SAE])¹, or the maximal allowable dose is reached. If a subject experiences a “clinically significant” AE attributable to SD-809 ER, the investigator will determine if a dose reduction or suspension is necessary. Subjects will have a telephone contact at Week 1 and a clinic visit at Week 2, in order to evaluate safety and establish a dose of study drug that adequately controls chorea and is well-tolerated. Although subjects will enter the Long term treatment period after Week 2, titration may continue through Week 8 to optimize dose level. Additional dose adjustments may be made after Week 8 if clinically indicated.

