Long-Term Treatment Period: During long term treatment, all subjects will be contacted by telephone at Week 3 (the first week of Long-term treatment period) and will return to the clinic on Weeks 4, 8, 15, 28 and every 13 weeks thereafter for evaluation of safety and chorea control. Switch subjects will have an additional telephone contact at Week 7. Rollover subjects will have an additional telephone contact at Week 5. Subjects who have not achieved a stable dose by the Week 4 visit (Switch subjects) or Week 5 telephone contact (Rollover subjects) may have unscheduled visits or telephone contacts in order to further adjust their dose upward or downward. Site interactions for dose adjustment should alternate between telephone contacts and clinic visits. During long-term treatment, further dose adjustments of SD-809 ER may be made, if necessary, but not more often than weekly. Dose adjustments should be based on all available information including the subject’s and caregiver’s reports of adverse events and chorea control, information from rating scales and all safety evaluations. Long term treatment will continue until SD-809 ER becomes commercially available in the U.S.

Post-Treatment Safety Follow Up: All subjects will discontinue study drug at the End of Treatment visit and return for their final clinic visit one week later for evaluation of safety, cognition, behavior, chorea and motor function. During this one week washout, subjects should not take prohibited concomitant medications. After the one week washout is complete, concomitant medication use is per the discretion of the investigator. Subjects will also have a follow up telephone contact four weeks after their last dose of study drug, to evaluate adverse events and concomitant medication usage.

PK Sub-Study: A sub-study will be conducted to evaluate the pharmacokinetics (PK) of tetrabenazine and SD-809 ER in Switch subjects. Approximately 12 subjects will have rich PK sampling and approximately 24 subjects will have sparse PK sampling (See Section 6.8). The

¹ See Section 7 for evaluation of AEs regarding severity, relationship to study drug and definition of SAE.

PK of tetrabenazine and metabolites will be assessed at the Baseline visit and the PK of SD-809 ER and metabolites will be assessed at the Week 8 visit. If a subject requires a dose change at Week 8, the Week 8 visit assessments should be conducted except for PK sampling which should be postponed until Week 15.

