Subjects Enrolled from the SD-809-C-15 Study (Rollover): Subjects who have successfully completed Study SD-809-C-15 may be eligible to rollover directly into this study after they complete a 1-week washout period and the Week 13 evaluation of Study SD-809-C-15. To reduce subject burden, the Week 13 evaluation will provide some Baseline data for the present study. Additional evaluations required as part of the SD-809-C-16 study may be completed on the same day as the Week 13 visit of the SD-809-C-15 study after SD-809-C-16 informed consent/assent is obtained. If subjects are unable to enroll at the Week 13 visit they will have up to 3 weeks to complete the additional evaluations for Baseline or the subject will not be eligible to enroll in this study. In addition, following informed consent/assent, prior data from Study SD-809-C-15 can be used in this study as part of the subject’s medical history information.

As Rollover subjects will have discontinued study drug (SD-809 or placebo) for at least 1 week at completion of the SD-809-C-15 study, they will undergo titration on SD-809. During titration, the Investigator, in consultation with the subject and caregiver, will determine when an adequate level of chorea control has been achieved. The dose of SD-809 may be adjusted (upward or downward), in increments of 6 mg per day (each week) (6 mg/day or up to 12 mg/day after a total daily dose of 48 mg is reached), until there is adequate control of chorea, the subject experiences a protocol defined “clinically significant” adverse event, as outlined above, or the maximal allowable dose is reached. If a subject experiences a “clinically significant” AE attributable to SD-809, the Investigator will determine if a dose reduction or suspension is necessary. Although subjects will enter the long-term treatment period after Week 2, titration may occur through Week 8 to optimize dose level. Additional dose adjustments may be made after Week 8 if clinically indicated.

Long-Term Treatment Period: During long-term treatment, further dose adjustments of SD-809 may be made, if necessary, but not more often than weekly. Dose adjustments should be based on all available information including the subject's and caregiver's reports of adverse events and chorea control, information from rating scales, and all safety evaluations. The Long-Term Treatment Period will continue until SD-809 becomes commercially available in the U.S.

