9.5 Study Drug Exposure and Compliance

The Investigator or designated study staff is responsible for monitoring the subject's compliance with study drug during the trial. Compliance will be assessed by tablet count obtained from returned study drug containers and must be reviewed at every visit while the subject is still in the clinic to determine if the subject is taking study drug as directed.

Percent compliance in the interval between visits will be calculated as $100 \cdot (\text{number of tablets used} / \text{number of tablets expected to be used})$, where $\text{number of tablets used} = \text{number of tablets dispensed} - \text{number of tablets returned}$. A subject will be deemed compliant if the subject has taken 80% to 105% of the expected number of tablets of study drug; this definition of compliance supersedes the definition specified in the study protocol.

For Switch subjects, percent compliance will be summarized for the following time periods using descriptive statistics: from Day 1 to the Week 4 visit, from Day 1 to the Week 8 visit, and from Day 1 to the last dose of study drug. For Rollover subjects, percent compliance will be summarized for the following time periods using descriptive statistics: from the Day 1 to the Week 8 visit and from Day 1 to the last dose of study drug. Compliance will be summarized for these same time periods using counts and percentages.

The length of time (in days) that each subject is exposed to SD-809 will be summarized using descriptive statistics. For subjects who complete the study through Week 8, the duration of time in days from Day 1 until the day of first receiving the SD-809 dose received at Week 8 (i.e., the duration of time to achieve a stable dose of SD-809) will be summarized using descriptive

statistics. For Switch subjects who complete the study through Week 8, the number and percentage of subjects who achieve a stable dose by Week 4 (i.e., received the same dose of SD-809 at Week 4 that they received at Week 8) will be presented.

For each subject, the initial dose, titrations, and investigator-initiated dose changes that occur during the study will be listed.

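### Time to stable dose takes the Week 8 dose as stable by definition, so a subject still being titrated at Week 8 is scored as already stable

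*SAP*

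**What the plan says.** The protocol lists time to stable dosing as a safety endpoint (Section 8.4) but does not define stable. SAP 7.2 supplies the definition: days from Day 1 "until the first day at which the subject was taking the dose level they were receiving at Week 8". SAP 9.5 repeats it as the time "from Day 1 until the day of first receiving the SD-809 dose received at Week 8" and sets who is summarised: "For subjects who complete the study through Week 8, the duration of time in days from Day 1". Descriptive statistics are planned.

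The only stability percentage is for Switch subjects. SAP 9.5 counts those who "received the same dose of SD-809 at Week 4 that they received at Week 8". There is no such check for Rollover subjects, and none for either cohort beyond Week 8.

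The dosing rules leave the dose open at that point. For Rollover subjects, Protocol 3.1 says "titration may continue through Week 8 to optimize dose level. Additional dose adjustments may be made after Week 8 if clinically indicated". Protocol Schedule of Events B and Section 6.3.2 both provide for dose evaluation and adjustment at the Rollover Week 8 visit. For all subjects in long-term treatment, "further dose adjustments of SD-809 ER may be made, if necessary, but not more often than weekly". In the PK sub-study, if a Switch subject "requires a dose change at Week 8, the Week 8 visit assessments should be conducted except for PK sampling", the sampling moves to Week 15.

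**The concern.** The Week 8 dose serves as both the reference and the evidence of stability. Anyone on drug at Week 8 has met the rule, whatever happens next. The definition has no minimum time on an unchanged dose, no forward check, no censoring and no category for a subject who has not settled.

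This endpoint is the plan's direct measure of how long titration and conversion take, and evaluating titration is part of the first study objective. A subject still being raised at Week 8 is among the slowest to settle. The rule gives that subject a completed time on an intermediate step, so for continuing upward titration the error is always towards too short a time. The same calendar assumption underlies SAP 8.8, which calls all treatment from Week 8 the Stable-Dose Period.

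**Working it through.** The documents give no expected time to stable dose, so there is no planned figure to reproduce. The check applies the SAP rule to dose paths that the protocol allows.

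**Inputs.** Rollover start 6 mg/day, weekly steps of 6 mg/day, and 6 or 12 mg/day once 48 mg/day is reached (Protocol 5.2.3). Maximum 72 mg/day without a strong CYP2D6 inhibitor (Protocol 5.2.1). Week 8 target is Day 56 (SAP 8.9, Table 3).

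**Path to Week 8.** After k weekly steps the dose is 6 + 6k mg/day, starting on Day 1 + 7k. At k = 7 this is 6 + 42 = 48 mg/day from Day 1 + 49 = 50. The next step starts on Day 1 + 56 = 57. On this path the subject comes to the Day 56 visit on 48 mg/day.

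**Two readings.** The dose received at Week 8 may be the dose brought to the visit (first taken on Day 50) or the dose set at the visit (first taken on Day 57). The error is the day the final dose starts minus the day scored.

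| Final dose, steps after 48 mg | Final dose starts | Error, dose brought to visit | Error, dose set at visit |
|---|---|---|---|
| 54 mg, one 6 mg step | Day 57 | 57 − 50 = 7 | 57 − 57 = 0 |
| 60 mg, one 12 mg step | Day 57 | 57 − 50 = 7 | 57 − 57 = 0 |
| 72 mg, two 12 mg steps | Day 64 | 64 − 50 = 14 | 64 − 57 = 7 |
| 72 mg, four 6 mg steps | Day 78 | 78 − 50 = 28 | 78 − 57 = 21 |

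The one-day addition in the SAP 8.7 duration formula shifts both days equally and does not change these errors.

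**Slower path.** Weekly steps at Weeks 6 and 7 need unscheduled contacts. With adjustments only at the scheduled Rollover contacts (Weeks 1 to 5, then Week 8), 36 mg/day starts on Day 36, and a rise to 42 mg/day at the Week 8 visit starts on Day 57. On the first reading the subject is scored 57 − 36 = 21 days early, even if 42 mg/day proves final. On the second reading the error is 0.

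**Later changes have no effect.** Take two subjects who both reach 30 mg/day on Day 29. One stays there. The other changes dose on Days 60, 74 and 110. Both score 29 − 1 = 28 days (29 with the one-day addition), although the second subject's last change comes 110 − 1 = 109 days after Day 1.

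**The case against.** The Week 8 anchor is not arbitrary. Rollover titration is planned for up to eight weeks. Protocol 6.2 expects the dose to be established when titration ends, and Section 6.3.2 expects Rollover subjects to stay on their long-term dose after Week 8 unless a change is clinically indicated. The SAP rule is prespecified, reproducible and printed beside its label, and no formal testing is planned (SAP 8.1). All of this stands. It explains the choice of week, but it does not make a mid-titration dose stable.

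A reader might infer three stronger things that the documents do not support:

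- **That the report will show every subject as stable.** No such percentage is planned. SAP 9.5 summarises the duration, and its one percentage, the Switch Week 4 to Week 8 comparison, can fall below 100%.
- **That later dose changes will be hidden.** SAP 9.5 lists dose changes throughout the study. SAP 9.8 summarises dose, and the percentage at each dose level, by visit. SAP 9.9.1 tabulates adverse events leading to dose reduction or suspension by period. A drift after Week 8 would be visible there. It would not correct the endpoint.
- **That many subjects are mis-scored.** No re-titration rate is given. If 10% to 30% of about 80 Rollover subjects were re-titrated, that would be 8 to 24 people, but the range is purely an assumption. A late change made for another reason, such as disease progression, would not make the earlier time wrong.

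The larger errors in the table also depend on which Week 8 dose is meant, and the SAP does not say.

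**Conclusion.** The point holds. For subjects who complete Week 8, the rule always returns a time at about Week 8 or earlier and cannot record that the dose had not settled. For a Rollover subject raised weekly by 6 mg and heading for 54 to 72 mg/day, the time is 7 to 28 days too short on the first reading and 0 to 21 days on the second.

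These figures assume a Week 8 visit on Day 56, weekly increases without a break, and no strong CYP2D6 inhibitor (with one, the maximum is 42 mg/day). How many subjects follow such paths is unknown, so the effect on the reported mean or median cannot be sized. The harm is to the interpretation of one descriptive endpoint. It still deserves correction, because the rule gives wrong times for identifiable subjects and the data to flag them are already planned. A dose left and resumed before Week 8 is a separate matter and is not counted here.

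**What to change.** In SAP 7.2 and 9.5:

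1. State that the Week 8 dose is the dose in force after any adjustment made at the Week 8 visit.
2. For both cohorts, report the number and percentage whose dose was not changed at the Week 8 visit and stayed unchanged through the Week 15 visit. This extends the existing Switch Week 4 to Week 8 check.
3. In the time-to-stable-dose summary, treat subjects who fail this check as not stable by Week 8, censor them at Week 8 and use Kaplan-Meier.
4. Say how subjects who leave between Weeks 8 and 15 are classified, for example by their last recorded dose, with the number shown.

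The cost is SAP wording and a little programming on dose records already planned for listing and by-visit summary. No new data are needed. There are two drawbacks. A late change for an unrelated reason, such as starting an interacting drug, counts as not stable unless flagged. Times beyond Week 8 are still not estimated: the change stops slow subjects being scored as finished, but does not recover the missing days.
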